3.2 Number of Sites

The study will be conducted at approximately 4 to 6 sites in the United States and Australia. Sites that do not enroll subjects into an open cohort within 4 months of site initiation may be terminated and replaced.

Approved

3.3 Number of Subjects

Participants in this clinical investigation shall be referred to as “subjects”. Subjects with relapsed or refractory multiple myeloma is eligible for this study. Up to 60 evaluable subjects will be enrolled at approximately 4-6 clinical centers in the US and Australia. In the dose exploration cohorts, approximately 40 subjects will be enrolled. Up to 6 subjects will be enrolled at the MTD or highest tested dose to gain additional safety and PK information. In the expansion cohorts, up to 20 subjects will be enrolled and treated with MTD or highest tested dose of AMG 224. The rationale for the number of subjects required is detailed in [Section 10](#).

3.4 Replacement of Subjects

During dose exploration, subjects that are not DLT-evaluable will be replaced. A subject is not DLT-evaluable if the subject discontinues treatment for any reason other than a DLT prior to completing the first 28 days of AMG 224 treatment or does not receive 2 doses of AMG 224 during the 28-day DLT window. Additional subjects may be enrolled if Amgen’s medical monitor determines that the minimum required numbers of subjects with evaluable tissue samples have not been enrolled.

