Dose escalation decisions will be made in accordance with a 3+3 design modified to allow flexibility in the initial cohort size (decision rules noted in Table 1). Dose escalation will occur at the planned dose levels until the MTD is determined or until the highest dose level is tested. The MTD is defined as the highest dose level with an observed incidence of DLT in < 33% of subjects enrolled in a cohort dose level. At least 6 subjects will be treated at the MTD or highest tested dose.

Table 1. 3+3 Dose Level Decision Rules

#Subjects ^a	#Subjects with DLT	Decision
3-4	1	Enroll 2-3 additional subjects at same dose level
3-4	0	Escalate ^b
3-4	≥ 2	De-escalate ^c
6	1	Escalate ^b
6	≥ 2	De-escalate ^c

^a Subjects who are not DLT-evaluable (see Section 3.4) are excluded from the count of subjects

^b If final dose level has been reached, accrual will be suspended.

^c If 6 subjects already entered at next lower dose level, the estimated MTD has been established.

Part 2 – Dose Expansion:

In the Part 2 of the study up to 20 subjects with relapsed or refractory multiple myeloma will be treated. Subjects will be divided into the following 2 groups based on the status of prior treatment with CD38 targeting antibody (eg, Daratumumab):

- Group A will consist of subjects who had prior treatment with a CD38 targeting antibody (at least 10 subjects).
- Group B will consist of subjects who are naïve to CD38 targeting antibody treatment (approximately 10 subjects).

A body weight-based dosing will be evaluated in the Dose Expansion part of the study. Subjects will be treated with preliminary MTD identified from the Dose Exploration part of the study [REDACTED] adjusted for their body weight. Subjects with grade 2 thrombocytopenia at baseline (ie, platelet count < 75 to 50 x 10⁹/L) should be started at

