- If a subject permanently ended the study treatment before completion of DLT evaluation period for a reason other than experiencing a DLT, then another subject will be recruited to replace this subject for the evaluation of the MTD.

Dose escalation will occur at the planned dose levels until the MTD is determined or until the highest dose level is tested. The MTD is defined as the highest dose level with an observed incidence of DLT in $< 33\%$ of subjects enrolled in a cohort dose level. At least 6 subjects will be treated at the MTD or highest tested dose.

A DLT will be defined as any of the events described under ([Section 6.2.1.6](#)), occurring in a subject during the DLT window, and regarded by the investigators and/or Amgen medical monitor to be related to AMG 224. The DLT window will be the initial 28 days of treatment with AMG 224. The DLT window may also be extended to assess events starting within the window in case the DLT definition is time dependent (neutropenia or thrombocytopenia, see below). Any adverse event occurring outside the DLT window that is determined by the investigator to be possibly related to the investigational product, which is seen more frequently or is more severe than expected or is persistent despite appropriate management, can be determined to be a DLT upon unanimous decision by the DLRT after review of the adverse event and all available safety data. The CTCAE version 4.0 will be used to assess the severity of toxicities/adverse events. The DLRT may request additional reviews or recommend modifying or suspending the study if safety concerns arise during the study. In the event that a need to modify or suspend the study is identified, this information will be communicated to investigators immediately, in accordance with Amgen procedures, and in compliance with prevailing guidance, including EMEA/CHMP/SWP/28367/07 (Guideline on strategies to identify and mitigate risks for first-in-human clinical trials with investigational medicinal products). Refer to [Section 10.3.2](#) for additional details regarding the DLRT.

Dose Exploration Stopping Rules

The DLRT may consider part 1 dose exploration complete if one of the following rules is met:

- The highest planned dose level is evaluated, MTD has not been defined and no DLTs occur at any dose level, in this case the maximum administrated dose (MAD) may be used for part 2.
- A total of 40 DLT-evaluable subjects have been enrolled.
- An MTD is identified.

Approved

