During the DLT-window, if the dosing is delayed for more than 7 days the subject will be removed from the study and will be replaced. After DLT-window, if the dosing is delayed for ≤ 3 weeks, the subject should resume the treatment as soon as possible if deemed safe by the investigator. The investigator should inform the Amgen Clinical team as soon as the unexpected dosing interruption occurs. If the dosing of AMG 224 is delayed more than 3 weeks (missing 1 cycle) due to treatment-related adverse events, the subject will be removed from the study. If the dosing delay occurred under conditions other than those associated with AMG 224 related toxicities, the case will be reviewed by Amgen medical monitor to determine whether the subject will be allowed to resume AMG 224 treatment.

Rules for Withholding or Restarting

AMG 224 should be withheld for any of the following:

- Suspected DLT (including AE that meet DLT definition outside DLT window)
- Grade 3 thrombocytopenia (follow the thrombocytopenia management in [Section 6.3.1](#))
- Aspartate aminotransferase (AST) or alanine aminotransferase (ALT) greater than 3x ULN or total bilirubin greater than 1.5x ULN

AMG 224 dosing can be resumed if the toxicities resolve to grade ≤ 1 or return to subjects' baseline values. The restarting of therapy should be deemed safe by the investigators and Amgen's medical monitor.

Rules for Permanent Discontinuation

Subjects will permanently discontinue from the investigational product if:

- Subjects experience adverse events meeting the DLT criteria at any time. Subjects will be followed until the DLT is resolved, returns to baseline value or is considered stable. Subjects will be withdrawn from AMG 224 treatment and will be treated as deemed appropriate by the investigator or treating physician. Except for:
 - Subjects showing evidence of response or subjects who in the opinion of the investigator may be responding to AMG 224, may have the option to continue therapy once the adverse events recover to baseline or Grade 1 and the re-introduction of AMG 224 is deemed safe by the investigator, Amgen's medical monitor, and Global Safety Officer. The subject should

restart at a reduced dose (see [Section 6.2.1.4](#)) subsection Dose Adjustments).

- Intolerability of the study treatment
- The dosing is delayed > 3 weeks due to AMG 224-related adverse events
- Disease progression according to IMWG response criteria
- Clinical significant deterioration of health status

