Appendix H. Peripheral Neuropathy Assessment

TNSr Items	0	1	2	3	4
Symptom extension (tingling, numbness, neuropathic pain) ^a	None	Symptoms limited to fingers or toes	Symptoms extend to ankle or wrist	Symptoms extend to knee or elbow	Symptoms above knees or elbows or functionally Disability
Pin sensibility	Normal	Reduced in fingers/toes	Reduced up to wrist/ankle	Reduced up to elbow/knee	Reduced up to above elbow/knee
Vibration sensibility	Normal	Reduced in fingers/toes	Reduced up to wrist/ankle	Reduced up to elbow/knee	Reduced up to above elbow/knee
Strength ^b	Normal	Mild weakness	Moderate weakness	Severe Weakness	Paralysis
Tendon reflexes	Normal	Ankle reflex reduced	Ankle reflex absent	Ankle reflex absent/others reduced	All reflexes absent

^a The worse score of the 3 subcomponents (tingling/paresthesia, numbness, and neuropathic pain proximal extension) was used as the subjective symptom extension score.

^b The muscle with the worse score is used as the strength score (toe, ankle, wrist and finger extensors and flexors, quadriceps, hamstrings, biceps, and triceps). TNSr and pain items were adapted with permission [Lavoie Smith, 2010]sss

Approved

Amendment 4

Title: A Phase 1 First in Human Study Evaluating the Safety, Tolerability, Pharmacokinetics and Pharmacodynamics of AMG 224 in Subjects With Relapsed or Refractory Multiple Myeloma

Amgen Protocol Number AMG 224 20130314

Amendment Date: 16 July 2018

Rationale:

The purpose of this protocol amendment is to implement changes needed regarding dosage delays, weight-based dosing, maximum dose allowed, and dose adjustments.

These changes were included in protocol amendment 3; however, protocol amendment 3 was not implemented because the FDA did not agree with the plan for frail subjects. To implement these changes without the plan for frail subjects, this new amendment was needed.

Dosing delay changes were made to allow subjects who have a second dose delayed for more than 48 hours but could still have the second dose of IP within the 28-day DLT-window. This change will allow those subjects to still be DLT evaluable.

Weight-based dosing changes were made to provide clarification to sites how subject weight should be taken in preparation for weight-based dosing.

After protocol amendment 2 was approved, the maximum dose allowed was determined to be [REDACTED]. The maximum dose allowed was added to this protocol to ensure subject safety.

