Dose escalation decisions will be made in accordance with a 3+3 design modified to allow flexibility in the initial cohort size (decision rules noted in [Table 1](#)). Dose escalation will occur at the planned dose levels until the MTD is determined or until the highest dose level is tested. The MTD is defined as the highest dose level with an observed incidence of DLT in < 33% of subjects enrolled in a cohort dose level. At least 6 subjects will be treated at the MTD or highest tested dose.

Table 1. 3+3 Dose Level Decision Rules

#Subjects ^a	#Subjects with DLT	Decision
3-4	1	Enrol 2-3 additional subjects at same dose level
3-4	0	Escalate ^b
3-4	≥ 2	De-escalate ^c
6	1	Escalate ^b
6	≥ 2	De-escalate ^c

^a Subjects who are not DLT-evaluable (see protocol Section 3.4) are excluded from the count of subjects

^b If final dose level has been reached, accrual will be suspended.

^c If 6 subjects already entered at next lower dose level, the estimated MTD has been established.

Part 2 – Dose Expansion:

In the Part 2 of the study up to 20 subjects with relapsed or refractory multiple myeloma will be treated. **Subjects will be divided into the following 2 groups based on the status of prior treatment with CD38 targeting antibody (eg, Daratumumab):**

- **Group A will consist of subjects who had prior treatment with a CD 38-targeting antibody (at least 10 subjects).**
- **Group B will consist of subjects who are naïve to CD 38-targeting antibody treatment (approximately 10 subjects).**

A body weight based dosing will be evaluated in the Dose Expansion part of the study. Subjects will be treated with preliminary MTD identified from the Dose Exploration part of the study (██████) adjusted for their body weight. Criteria for adjustment in dosing based on stages of thrombocytopenia will be implemented as explained in the protocol.

In the Part 1 of the study a fixed dosing (ie, dose not adjusted for individual subject's body weight) will be evaluated and in the Part 2 of study body weight based dosing will be evaluated. When sufficient AMG 224 clinical data becomes available, a full assessment of body size effect on PK/PD will be conducted to determine the optimal dosing approach prior to conducting the registration trial for AMG 224 in multiple myeloma patients.

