6.3 Dose Limiting Toxicity Evaluable Analysis Set

The analysis of DLT will be restricted to DLT-evaluable subjects. A subject is not DLT-evaluable if he / she discontinues treatment for any reason other than a DLT prior to completing the first 28 days of AMG 224 treatment or does not receive 2 doses of AMG 224 during the 28 day DLT window.

7. Planned Analyses

The Planned analysis is described in following sections.

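### The DLT-evaluable definition exempts DLTs in its discontinuation clause but not in its two-dose clause, so a subject whose DLT prevents dose 2 literally drops out of the DLT incidence and the final MTD model

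*Protocol*

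**What the plan says.** Protocol 3.4 says that a subject is not DLT-evaluable if treatment stops, for a reason other than a DLT, before the first 28 days are complete, "or does not receive 2 doses of AMG 224 during the 28-day DLT window". SAP 6.3 uses the same two grounds for the DLT Evaluable Analysis Set. Its second ground reads "does not receive 2 doses of AMG 224 during the 28 day DLT window".

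The definition is then used as follows:
- **3+3 rules.** Table 1, footnote a, in Protocol 3.1 says "Subjects who are not DLT-evaluable (see Section 3.4) are excluded from the count of subjects". SAP 3.1 has the matching footnote.
- **DLT incidence.** Protocol 10.1.2 and SAP 9.6.1.2 restrict the DLT analysis to evaluable subjects.
- **TPI model.** Protocol 10.4.2.3 and SAP 9.6.1.2 fit it to DLT-evaluable subjects from both parts, after 5 expansion subjects and again at the end.

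Dose 2 falls on Day 22 (Protocol Table 5 footnotes). Protocol 6.2.1.5 withholds drug for a suspected DLT. It also lists "Subjects experience adverse events meeting the DLT criteria at any time" as a ground for permanent discontinuation, with an exception for subjects who respond or may be responding.

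Other text points the other way. Protocol 6.2.1.2 replaces a subject who stops "before completion of DLT evaluation period for a reason other than experiencing a DLT". The Amendment 4 rationale treats the two-dose condition as a matter of delayed dosing: of its longer permitted delay it says "This change will allow those subjects to still be DLT evaluable".

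**The concern.** The two grounds are alternatives, so being excepted under the first gives no protection under the second. A subject who has a DLT in the first three weeks and is then managed as Protocol 6.2.1.5 directs may receive only one dose. Read literally, that subject is not evaluable because of the very event the analysis is meant to count.

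The error runs one way: it removes DLTs, so the DLT rate is biased down and the MTD up. DLT incidence is part of the primary endpoint and the MTD is a primary objective. No other provision puts the subject back. The sensitivity analysis in Protocol 10.4.2.3 (optional in SAP 9.6.1.2) adds only DLTs outside the window, and SAP Section 10 declares no departures from the protocol.

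**Working it through.** **1. The plan's own figures.** Protocol 10.2 gives the chance of at least one DLT at true rates of 10% and 33%. With 1 − (1 − p)^n:
- n = 3: 27.1% and 69.9% (stated: 27 to 70%)
- n = 6: 46.9% and 91.0% (stated: 47 to 91%)

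These reproduce, but they assume that every DLT is counted.

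**2. Reported rate under the literal rule.** Let p be the true DLT rate and f the share of DLT subjects who miss dose 2. The documents give no f, so 0, 0.25 and 0.5 are assumed. The rate among evaluable subjects is q = p(1 − f)/(1 − pf).

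| True p | f = 0 | f = 0.25 | f = 0.5 |
|---|---|---|---|
| 0.33 | 0.330 | 0.270 | 0.198 |
| 0.25 | 0.250 | 0.200 | 0.143 |

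For p = 0.33 and f = 0.5: 0.165/0.835 = 0.198. At p = 0.33 the chance of seeing at least one DLT falls from 70% to 61% or 48% (n = 3), and from 91% to 85% or 73% (n = 6).

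**3. TPI illustration.** Inputs:
- Model and prior from SAP Appendix A: logit(p) = log α + β log(d/d_max), with (log α, log β) bivariate normal, means 0.0536 and −0.1469, SDs 1.685 and 1.001, correlation −0.216.
- Limit from Protocol 10.4.2.3: the probability that the DLT rate exceeds 0.35 must be below 0.25.
- Assumed, because most doses and all cohort counts are unavailable: 0/3 at 30 mg, 0/6 at 105 mg, d_max = 300 mg (top of the stated range), and the Part 2 dose equal to d_max.
- Exploration at that dose fixed at 0/6 or 1/6, because a preliminary MTD requires fewer than 33% DLTs.
- Each expansion subject has a DLT with probability 0.33. Each DLT subject is dropped from numerator and denominator with probability f.

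Posterior probability of a rate above 0.35 (exploration and expansion combined at the test dose):

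| DLTs/subjects | Probability | Below 0.25? |
|---|---|---|
| 3/11 | 0.210 | yes |
| 4/11 | 0.417 | no |
| 3/10 | 0.268 | no |
| 8/26 | 0.256 | no |
| 7/25 | 0.174 | yes |
| 9/26 | 0.401 | no |
| 8/25 | 0.301 | no |
| 7/24 | 0.210 | yes |

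At the final fit, one lost DLT turns 8/26 (fails) into 7/25 (passes). Two lost DLTs turn 9/26 (fails) into 7/24 (passes).

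Chance that the dose passes the limit:

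| Fit | Exploration | f = 0 | f = 0.25 | f = 0.5 |
|---|---|---|---|---|
| First (5 expansion) | 0/6 | 0.96 | 0.97 | 0.99 |
| First (5 expansion) | 1/6 | 0.80 | 0.82 | 0.89 |
| Final (20 expansion) | 0/6 | 0.67 | 0.89 | 0.98 |
| Final (20 expansion) | 1/6 | 0.49 | 0.76 | 0.93 |

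The first-fit change is 1 to 9 points. The final-fit change is 22 to 44 points.

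**4. 3+3.** Escalation probability is (1 − q)³ + 3q(1 − q)⁵. At p = 0.33 it is 0.43, 0.56 and 0.71 for f = 0, 0.25 and 0.5, if the literal count is followed with no override.

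**The case against.** The strongest reply is that this is a drafting slip whose intent is plain. The first ground keeps subjects who stop for a DLT, Protocol 6.2.1.2 replaces only those who stop for another reason, and the 3+3 rules presuppose that DLTs count. Sensible staff may count these subjects anyway. That is fair, and it lowers the grade. It does not amend the definition of the set used for a primary endpoint, and overriding the definition after data are seen would be an undocumented departure from the SAP.

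A reader might infer more than the documents support:
- **That every early DLT is lost.** A subject who recovers and receives dose 2 by Day 28, or whose DLT follows dose 2, stays evaluable.
- **That escalation was compromised.** Protocol 10.3.1 and SAP 7.1 have the dose level review team consider DLTs in all subjects. Amendment 2 reports no DLT with Cohort 6 reached, and Protocol 2.4.2 already names a preliminary MTD, so escalation appears largely complete.
- **That the first TPI fit is badly distorted.** Treating all 11 subjects at the dose as random at 33% gives 0.48, 0.56 and 0.74, but this ignores that the six exploration subjects must already have met the preliminary MTD rule. The fit also does not set the dose by itself; the review team decides.
- **That a dropped Part 2 subject cannot be replaced.** Protocol 3.4 limits replacement to dose exploration, but the delay rule in 6.2.1.5 removes and replaces subjects after a delay of more than 7 days in the window, without limiting this to Part 1. A replacement refills the denominator but does not restore the lost DLT.

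One further objection stands. Protocol 6.2.1.6 and SAP Section 5 define a DLT as an event in Part 1. Read as literally as the two-dose clause, an expansion subject has no DLT to lose. The final-fit argument therefore depends on Protocol 10.4.2.3 and SAP 9.6.1.2, which use expansion subjects in the DLT model. The two must be reconciled.

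**Conclusion.** The wording defect is real and appears in both documents. By the letter of the plan, a subject whose DLT prevents dose 2 leaves the DLT incidence and the TPI data, and nothing restores that subject. The effect on incidence needs no dose information: a true 33% is reported as about 27% or 20% if a quarter or a half of DLT subjects miss dose 2. In the illustration the effect on the final MTD estimate is large and that on the first fit small; the 3+3 effect carries little weight.

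These sizes rest on an assumed f, assumed doses and counts, and a Part 2 dose set equal to d_max, although Part 2 dosing is weight-based with a cap. Passing the limit is necessary, not sufficient, for a dose to be named the MTD. Adverse events in the dropped subjects would still appear in the Safety Analysis Set tables. This should be fixed; given the evident intent and the review team's access to all DLTs, it does not rank as a critical flaw.

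**What to change.** In Protocol 3.4 and SAP 6.3, define a DLT-evaluable subject as one who either had a DLT in the DLT window after any dose of AMG 224, or received 2 doses and completed the 28-day window without a DLT.

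Then:
- Reconcile the replacement wording in Protocol 3.4, 6.2.1.2 and the delay rule in 6.2.1.5, which has no DLT exception, so that a subject with a DLT is counted and not replaced.
- Reconcile the Part 1 restriction in the DLT definition (Protocol 6.2.1.6, SAP Section 5) with the use of expansion subjects in the TPI model (Protocol 10.4.2.3, SAP 9.6.1.2).

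The cost is one sentence in each document plus aligned wording and cross-references. No extra subjects or data are needed. The change affects counting only, not dosing.

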6.2.1.6 Dosage Limiting Toxicities

The grading of adverse events will be based on the guidelines provided in the Common Terminology Criteria for Adverse Events (CTCAE) version 4.0 (available online at <http://evs.nci.nih.gov/ftp1/CTCAE/About.html>). Determination of the severity of adverse events will be consistent with Common Terminology Criteria for Adverse Events (CTCAE) version 4.0. The relationship of an adverse event to investigational product will be determined by the Investigator. An event should be considered related to treatment if, in the Investigator's medical judgment, there is a reasonable possibility that the event may have been caused by AMG 224.

A DLT is defined as a Grade 3 or higher non-hematological or a Grade 4 hematologic adverse event that occurs during the DLT window (day 1 through day 28 after the administration of the first dose of AMG 224) in Part 1 Dose Exploration unless clearly attributable to causes other than AMG 224 treatment. DLT toxicities do not include fatigue, nausea, diarrhea, vomiting, neutropenia, anemia, thrombocytopenia and lymphopenia, increased serum creatinine or electrolytes abnormalities that are not clinically significant and require no treatment unless the following criteria are met:

Hematological toxicity:

- Grade 4 neutropenia lasting > 7 days
- Grade 3 or 4 neutropenia with fever > 38.5°C
- Grade 3 thrombocytopenia with ≥ Grade 2 hemorrhage
- Grade 4 thrombocytopenia lasting > 7 days
- Grade 3 anemia with symptoms or required intervention (eg, transfusion)
- Grade 4 anemia
- Lymphopenia of any grade is not considered a DLT

Approved

Non-hematological toxicity:

- \geq Grade 3 nausea, vomiting or diarrhea persisting more than 3 days despite optimal medical support
- Grade 3 fatigue persisting > 7 days
- \geq Grade 3 acute kidney injury (creatinine >3 X baseline or > 4.0 mg/dL) lasting > 3 days
- Elevation of either AST or ALT according to the following criteria:
 - $> 8x$ ULN;
 - $> 5x$ ULN but $< 8x$ ULN for ≥ 2 weeks;
 - $> 5x$ ULN but $< 8x$ ULN and unable to adhere to enhanced monitoring schedule; or
 - $> 3x$ ULN with clinical signs or symptoms that is consistent with hepatitis (such as right upper quadrant pain/tenderness, fever, nausea, vomiting, jaundice, rash or eosinophilia ($> 5\%$)).
- TBIL $> 3x$ ULN

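### Subjects whose second dose is blocked by drug toxicity below the DLT threshold are left out of the DLT rate and the TPI model; the exclusion is informative, and the plan neither counts nor bounds its effect on the MTD

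*Protocol*

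**What the plan says.** **Evaluability.** Under Protocol 3.4 a subject is not DLT-evaluable on either of two grounds: stopping treatment in the first 28 days for a reason other than a DLT, "or does not receive 2 doses of AMG 224 during the 28-day DLT window". The second ground has no exception for drug toxicity. SAP 6.3 has the same rule: a subject is out who "does not receive 2 doses of AMG 224 during the 28 day DLT window". The consequence in Part 1 is stated in 3.4: "During dose exploration, subjects that are not DLT-evaluable will be replaced".

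**Delay.** Protocol 6.2.1.5 adds, for the DLT window, that "if the dosing is delayed for more than 7 days the subject will be removed from the study and will be replaced". This too makes no exception for toxicity.

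**Withholding.** The same section withholds AMG 224 for "Grade 3 thrombocytopenia (follow the thrombocytopenia management in" Section 6.3.1), and for "Aspartate aminotransferase (AST) or alanine aminotransferase (ALT) greater than 3x ULN or total bilirubin greater than 1.5x ULN". The general restart condition is recovery to Grade 1 or better, or to baseline.

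**DLT threshold.** Under 6.2.1.6, Grade 3 thrombocytopenia is a DLT only with Grade 2 or worse hemorrhage. For Grade 4 the criterion is "Grade 4 thrombocytopenia lasting > 7 days". AST or ALT between 3 and 5 times ULN, without symptoms and without the bilirubin rise of a Hy's Law case, meets none of the listed liver criteria.

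**Use of the set.** Footnote a of Table 1 (Protocol 3.1) leaves non-evaluable subjects out of the 3+3 count. Protocol 10.4.2.3 and SAP 9.6.1.2 fit the TPI model, which gives the final MTD, to DLT-evaluable subjects only.

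**The concern.** There is a gap between toxicity that stops dose 2 and toxicity that counts as a DLT. A subject with Grade 3 platelets at Day 22 and no bleeding, not recovered by Day 28, has no DLT, receives no second dose and leaves the analysis. The missingness is caused by the drug. It comes from the two toxicities that Protocol 2.3 anticipates, thrombocytopenia and hepatotoxicity, and it would be expected to grow with dose.

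Protocol 2.4.2 chose the three-weekly interval from the recovery of thrombocytopenia with related conjugates, so failure to recover in time for dose 2 bears directly on whether a dose can be given on schedule. The evaluable set is selected for subjects who tolerated dose 1. An MTD estimated from it describes that selected group, and the reader is not told how many subjects were left out at each dose, or why.

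**Working it through.** **The plan's own figures.** Protocol 10.2 gives the chance of at least one DLT at true rates of 10% to 33%. Using 1-(1-p)^n: for n = 3, 27.1% and 69.9% (stated 27 to 70%); for n = 6, 46.9% and 91.0% (stated 47 to 91%). They reproduce.

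**Inputs.** Let p be the probability of a DLT per treated subject, and q the probability of no DLT but dose 2 blocked by drug toxicity. The values of p below lie within the range in Protocol 10.2. The documents give no rate for q, so q is an assumption, shown from 5% to 30%.

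**Escalation.** For Table 1 with three initial subjects and a DLT rate x in the count:

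E(x) = (1-x)^3 + 3x(1-x)^2 × (1-x)^3

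**Three handlings of the blocked subject.** Excluded and replaced, as planned: x = p/(1-q). Kept as a non-event: x = p. Counted as an event: x = p+q.

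| p | q | Observed rate, as planned | E, as planned | E, kept as non-event | E, counted as event |
|---|---|---|---|---|---|
| 10% | 5% | 10.5% | 89.7% | 90.6% | 81.4% |
| 10% | 10% | 11.1% | 88.7% | 90.6% | 70.9% |
| 10% | 20% | 12.5% | 86.2% | 90.6% | 49.4% |
| 10% | 30% | 14.3% | 82.8% | 90.6% | 30.9% |
| 20% | 5% | 21.1% | 68.6% | 70.9% | 60.0% |
| 20% | 10% | 22.2% | 66.0% | 70.9% | 49.4% |
| 20% | 20% | 25.0% | 60.0% | 70.9% | 30.9% |
| 20% | 30% | 28.6% | 52.4% | 70.9% | 17.2% |

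The planned rule lies between the two bounds in every row. With four initial subjects the order is the same (p = 10%, q = 20%: 84.3%, 89.2%, 44.2%).

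**When the MTD is biased upward under the existing DLT definition.** Let r be the probability that a blocked subject would have had a DLT if both doses had been given. The two-dose DLT rate is p + qr; the observed rate is p/(1-q). Setting them equal gives qr = pq/(1-q), so r = p/(1-q). With p = 15% and q = 20%, the break-even is 0.15/0.80 = 18.75%.

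| r | Two-dose DLT rate | E at that rate | E as planned |
|---|---|---|---|
| 0 | 15% | 81.4% | 73.6% |
| 25% | 20% | 70.9% | 73.6% |
| 50% | 25% | 60.0% | 73.6% |
| 100% | 35% | 39.6% | 73.6% |

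Below the break-even the planned rule is conservative; above it, the rule is too permissive. The TPI model was not run, because the dose levels are redacted.

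**Dates.** Dose 2 is due on Day 22, and 22 + 7 = 29. A second dose that is seven days late is allowed by 6.2.1.5 but falls outside the Day 1 to 28 window of 3.4.

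**The case against.** A reader might infer that the toxicity drops out of the DLT rate and that the MTD is therefore pushed up. The documents do not support this. Under 6.2.1.6 the toxicity was never in the numerator. What leaves is a non-event in the denominator, so against the protocol's own definition the rate goes up and escalation becomes harder. A reader might also take 86.2% against 49.4% as the size of a bias. That contrast relabels every blocked dose as a DLT, so it compares two DLT definitions, and whether such toxicity should be dose-limiting is a clinical choice for the sponsor. Both corrections stand.

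The plan also has safeguards.
- The dose level review team (DLRT) sees all available data and all Grade 3 or worse toxicities below the DLT threshold, and may model thrombocytopenia risk (6.2.1.2, 10.3.2).
- Safety data from all enrolled subjects in preceding cohorts are considered (3.1).
- The window can be extended for time-dependent cytopenias, and a persistent related event outside it can be declared a DLT by unanimous decision (6.2.1.2).
- The rationale for Amendment 4 says the permitted delay was widened from 48 hours to 7 days so that subjects with a late second dose stay evaluable.
- SAP 9.2 and 9.6.2 already summarise analysis-set membership, discontinuation reasons and dose modifications, and the review listings in SAP Appendix A include dosing dates.

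These reduce the concern without closing it. Use of sub-threshold toxicity in dose decisions is optional. No output shows, by dose, who missed dose 2 because of the drug. The only DLT sensitivity analysis (10.4.2.3, SAP 9.6.1.2) covers events outside the window. Nothing returns these subjects to the TPI model.

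Finally, Protocol 2.4.2 already takes an expansion dose from the exploration data, so the escalation decisions may be largely past. What remains live is the TPI fit after five expansion subjects and the final MTD estimate. Replacement under 3.4 covers exploration only, so a blocked subject in expansion simply reduces the data for that fit.

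**Conclusion.** The exclusion is real, is the same in both documents, and is informative. Its direction is not determined by the documents. Against the stated DLT definition it raises the observed rate from p to p/(1-q). The MTD is biased upward only if inability to receive dose 2 is regarded as dose-limiting, or if blocked subjects would have had DLTs on full dosing at a rate above p/(1-q). An above-average risk is plausible in subjects who already have toxicity from dose 1, but it is not shown. All sizes rest on an assumed q, on independent subjects and on Table 1 applied without DLRT discretion. The case for a change is that a complete-case MTD estimate can be replaced, at little cost, by one with stated bounds.

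Two inconsistencies should be reconciled with it. Read literally, the second ground in 3.4 would also exclude a subject whose cycle 1 DLT prevented dose 2. A reader might infer that DLTs themselves are being discarded, but the first ground of 3.4 and the replacement rule in 6.2.1.2 both set DLTs apart, so this looks like a drafting gap. The other is the Day 29 and Day 28 mismatch.

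**What to change.** In Protocol 3.4 and 10.4.2.3 and SAP 6.3 and 9.6.1.2:

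1. Tabulate by dose level, for each DLRT meeting and for the final report, the subjects without a DLT who were not given dose 2 within Days 1 to 28 because of AMG 224-related toxicity, with the toxicity named.
2. Prespecify sensitivity analyses of DLT incidence and of the TPI model that keep these subjects in the denominator under both bounds, once counted as events and once as non-events, shown beside the main analysis.
3. Reconcile the second ground of 3.4 with 6.2.1.2 for subjects who have had a DLT, and the seven-day delay in 6.2.1.5 with the 28-day window in 3.4.

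Replacement and the DLT definition stay as they are. Items 1 and 2 cost one table and two more model runs. The drawback is that a sensitivity MTD may differ from the main one, in either direction, and the report would have to discuss it.
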